6.2.3 Blinding

Blinding will be maintained by using identical headphones and MP3 players for all subjects. The PI, any personnel involved in collecting the clinical outcomes (e.g., PIPP) or collecting or quantifying EEG outcomes, and the statistician will be blinded. The statistician will be aware of blinded treatment group, so that e.g. safety summaries by blinded treatment group can be prepared for the Data Safety and Monitoring Board (DSMB) closed sessions if it so requests. Should the DSMB request unblinded comparisons, the study team will contract with the University of Minnesota CTSI's Biostatistical Design and Analysis Center (BDAC) for an independent statistician to work with the DSMB using unblinded data.

The unblinded staff includes [name] (music therapist) and [name] (Director of the NICU). [name] will prepare the music players. Both will be unblinded to handle randomization, delivery of interventions, and preparations of unblinded reports to the independent study monitors. They will not be involved with data monitoring, analyses, or outcome assessments.

The study coordinators who are assessing the PIPP will wear earplugs and noise cancelling headphones, which will ensure that s/he cannot hear what is emanating from the infant's headphones. In addition, family members and NICU staff will be reminded frequently to not disclose what they think they hear coming from the infant's headphones.

6.2.4 Followup Visits: Visits 2-5 (See above table for timing of visits)

EEG: provides real time information about cerebral function by measuring cerebral electrical activity recorded from electrodes placed on the scalp. This EEG includes a video component that will be recording the child during the EEG, in order to assess if any movement was occurring during the EEG. **PIPP**: The Premature Infant Pain Profile is a 7-item multidimensional measure of pain that includes 3 behavioral (brow bulge, eye squeeze, nasolabial furrow), 2 physiological (heart rate, oxygen saturation), and 2 contextual

(gestational age and behavioral state) measurements. The measurements are scaled on a 4 point scale (0,1,2,3) with increasing change of each variable from baseline. The 7 items are summed for a total pain intensity score.

Visit 2 and 3:

- Vital Signs
- Concomitant Meds
- On Study Visit Checklist
- EEG
- PIPP
- Adverse Events
- SAE

Visit 4:

- Vital Signs
- Concomitant Meds
- On Study Visit Checklist
- EEG
- Adverse Events
- SAE
- Family Feedback** may be completed at visit 4 or any time before discharge from the hospital

Prior to discharge the study team will review the child's medical chart to collect the clinical BAER score. The BAER stands for the *Brainstem auditory* evoked response (*BAER*) test which evaluates a child's hearing and is done as part of clinical care. If the child does not pass while hospitalized, the clinical care team may conduct a follow-up BAER test at their clinical care follow-up appointment. For a child that has a follow-up BAER test, the study team will review the medical chart and collect this information to ensure that hearing is confirmed prior to the child's study ERP, as part of Visit 5/Completion Visit. If the child does not pass this 2nd hearing test, the PI may withdraw the family from the ERP portion of the study visit.

Visit 5/Completion Visit:

- Concomitant Meds
- Medical History
- Music Exposure
- On Study Visit Checklist
- Adverse Events
- SAE
- Study Completion
- ERP: Event related potentials quantify changes in electrical brain potentials timelocked in milliseconds with a stimulus and they are widely used to study cognitive abilities such as discrimination, attention, and memory.

Event related potential (ERP) testing will occur on follow-up at 43-48 weeks corrected gestational age in all subjects to evaluate early neurodevelopment.

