Updated protocol to reflect that ERPs will be conducted between 43-48 weeks corrected gestational age. See pgs 10,11,15,16, 26, 30. No impact on analysis. This allows for better compliance with allowing for scheduling families with a new born child.

Version Number 7.0

Version Date: February 1, 2022

Pg 20: Updated Section 6.1 Schedule of Evaluations – Screening and Study Visits to remove the 48 hour time period for baseline/visit 1 activities to occur. This change is administrative only as it has no impact on study aims, analysis or safety.

Version Number 8.0

Version Date: March 8, 2022

Pg 20-21: *Updated Section 6.1 Schedule of Evaluations &* Pg 25: *Section 6.2.4 Follow up Visits: Visits 2-5* to move Family Feedback form completion at Visit 4, noting though that this may be completed at any time prior to discharge.

TABLE OF CONTENTS

Page
FULL PROTOCOL TITLE
1 R61 A1010/12-01 1
Tool Revision History
TABLE OF CONTENTS 7
STUDY TEAM ROSTER
PARTICIPATING STUDY SITES
PRÉCIS 13
1. STUDY OBJECTIVES 14
1.1 Primary Objective (1) 14
1.2 Primary Objective (2) 15

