4.3 Study Enrollment Procedures_

Newborns will be recruited from the University of Minnesota Masonic Children's Hospital neonatal intensive care unit (NICU). We will ensure staff in the NICU are aware of the study and post flyers in the NICU to alert neonatology staff to the study's purpose, inclusion criteria, and the pager number needed to contact the study staff regarding potential subjects. The neonatologist will first mention the study to the parents, then ask whether the parents would be willing to further discuss the study with the study investigators. Only parents who express interest in learning about the research study will be approached regarding enrollment of their infant.

The PI and other selected study investigators listed on the IRB will obtain consent. All study investigators who will be obtaining consent will receive training on how to determine eligibility of subjects and how to discuss the study with parents. The study investigator who obtains consent will ensure the parents understand the informed consent process and the requirements of the study. Parents will be informed that they can ask questions about the study at any time and contact information for the study staff will be provided on the consent form.

Once eligibility has been confirmed and consent obtained, subjects will be randomly assigned to the MBI or control treatment cohorts in a 50:50 allocation ratio using randomization tables, stratified by sex and within each stratum use randomly allocated block sizes of 2 and 4, prepared by [name].

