9.2 Sample Size and Randomization

The R61 phase is exploratory. Based on the number of eligible infants and assuming 60% of eligible subjects enrollment, we can feasibly enroll 60 infants in 1.5 years.. This sample size is similar to or larger than other MBI studies in infants.^{21,23,68,107}

The clinical measure Premature Infant Pain Profile (PIPP) at 4 weeks is the primary outcome for the R61-phase pilot clinical trial. With expected recruitment of at least 60 preterms, expected 50 completed PIPPs at 4 weeks represents a loss to follow-up of $(60-50)/60 = \sim 17\%$. Such a loss rate is slightly more conservative than previous studies completed in the University of Minnesota NICU (which has had ~15% loss rates). This sample size is similar to or larger than other previous MBI studies in infants.

With 50 completed PIPPs at 4 weeks, for comparing MBI to control (25 per group), there is 80% power to detect a group difference in PIPP of 2.9 and 85% power to detect a group difference in PIPP of 3.1. These calculations assume a between-infant standard deviation of 3.6, estimated from the placebo group of a recent study of sucrose as an analgesic for pain from a standard-of-care heel lance. These calculations were carried out in SAS with the following code:

proc power;

twosamplemeans test=diff meandiff = . stddev = **3.6** npergroup = **25**

```
power = 0.80 0.85
    alpha = 0.05
run;
```

;

The R61 exploratory phase data from primary outcome clinical measure PIPP at 4 weeks will be utilized to assist in planning of the R33 phase. The associations of baseline characteristics (infant, e.g. birthweight, and maternal pregnancy history, etc) may inform the design of the R33 phase. For example, these secondary analyses might indicate that we should stratify randomization in the R33 phase by a dichotomized infant birthweight. These analyses, using linear models or non-parametric alternatives if needed (e.g., measures are highly skewed), will use both intervention groups and we will examine the magnitudes of associations in each group and, if appropriate, in the pooled groups.

Treatment Assignment Procedures

Once eligibility has been confirmed and consent obtained. Randomization will be accomplished through the use of randomization tables, stratified by sex and within each stratum use randomly allocated block sizes of 2 and 4. These will be prepared by the study statistician ([name]).

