9.5 Outcomes: Milestone Measures and Data Analyses

Measure 1: Average sleep (REM+nonREM) duration difference between MBI and controls using EEG. Normal preterm brain development is dependent on cycling between wakefulness and sleep with sleep durations gradually increasing by about 5% increments every two weeks until term age. EEG will be used to measure the average duration of sleep (REM + non-REM) between MBI and controls. Average sleep duration measurements will determine if MBI promotes/enhances brain maturation.

Statistical Analysis: Four quality sleep durations from within each EEG session will be averaged per-infant per-timepoint (one EEG session for each of the 4 age timepoints, 30 weeks, 32 weeks, 34 weeks, 36 weeks). At each timepoint, average sleep duration will be compared between MBI infants and controls. Milestone threshold will be reached if >5% longer average durations of sleep are found in the MBI cohort compared to controls in any 1 or more of the serial EEGs.

Measure 2: Late Slow Wave amplitude difference in auditory ERPs comparing MBI to controls. Due to immature nervous systems, early infant neurodevelopment studies have centered on attentional capture paradigms using ERPs. ERPs quantify changes in electrical brain potentials time-locked to a stimulus and are widely used to study cognitive abilities such as learning, discrimination, attention, and memory. At one month age, the ERP Late Slow Wave of a mom/stranger stimulus is considered a reflection of perceptual learning and memory. ERP Late Slow amplitude measurements will determine if MBI enhances neurodevelopment.

Statistical Analysis: ERP Late Slow Wave amplitudes from the 100 trials of the auditory recognition task will be averaged. Within-infant average Late Slow Wave amplitudes across mother's voice trials minus the same average across stranger's voice trials will be computed and averaged. Mother-vs-stranger Late Slow Wave average difference between MBI and controls will be compared. Milestone threshold will be reached if $\ge 1 \ \mu V$ greater amplitude difference in ERPs of the MBI cohort compared to controls is found at one month adjusted age.

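### The ERP milestone compares raw arm means over a 5-week test window, without age at test or sex in the analysis, so avoidable random error enters the estimate

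*Combined protocol and SAP*

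**What the plan says.** - **Timing.** Section 6.2.4: "Event related potential (ERP) testing will occur on follow-up at 43-48 weeks corrected gestational age in all subjects to evaluate early neurodevelopment". The schedule table in section 6 gives the same window, while visits 2 to 4 are held to ±3 days. The revision history entry for version 6.0 explains the window by the scheduling of families and adds "No impact on analysis".
- **Endpoint.** Section 9.5, Measure 2: "Within-infant average Late Slow Wave amplitudes across mother's voice trials minus the same average across stranger's voice trials will be computed and averaged".
- **Comparison.** Same place: "Mother-vs-stranger Late Slow Wave average difference between MBI and controls will be compared". The milestone is met if a difference of at least 1 µV, described as a "greater amplitude difference in ERPs of the MBI cohort compared to controls is found at one month adjusted age".
- **Balance.** Section 4.3: "subjects will be randomly assigned to the MBI or control treatment cohorts in a 50:50 allocation ratio using randomization tables, stratified by sex". Nothing in the design balances age at test.

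Measure 2 names no covariate, model, standard error or interval. The linear models mentioned in section 9.2 concern baseline characteristics and the planning of the R33 phase, not the ERP measure.

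**The concern.** The protocol uses the Late Slow Wave as a marker of perceptual learning and memory in early infancy. A marker of maturation may well change over five weeks at this age. If it does, spread in test age adds to the between-infant variance, and any chance difference in mean test age between the arms passes into the estimated effect.

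The decision rule is a point estimate set against 1 µV. The version 2.0b revision note gives the Go/NoGo criteria equal weight, and Measure 2 has only one timepoint, so no second reading can steady it. Removable noise therefore bears directly on one of the four milestones that inform the R33 phase. Leaving the analysis unspecified also leaves the choice about age open until the data are seen.

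**Working it through.** **The plan's own figure.** The documents contain no power calculation or SD for the ERP measure. The only calculation is for PIPP at 4 weeks (section 9.2), "for comparing MBI to control (25 per group"), SD 3.6, alpha 0.05. It reproduces: a noncentral t calculation gives 79.7% power at a difference of 2.9 and 84.7% at 3.1, against the stated 80% and 85%. Only its 25 per arm is carried forward.

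**Inputs**
- Window 43–48 weeks, 5 weeks wide (section 6.2.4).
- Completers: 25 per arm. This is an assumption borrowed from PIPP; ERP completion may differ.
- Test ages uniform over the window: assumption.
- Change of the mother-minus-stranger difference with age: 0.25, 0.5 and 1.0 µV per week. Assumption; the documents give none.
- Between-infant SD of that difference: 2 to 10 µV. Assumption; the documents give none.

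**Step 1: chance difference in mean age**
- SD of age = 5/√12 = 1.443 weeks.
- SE of the arm difference = 1.443 × √(2/25) = 0.408 week.
- Typical (mean absolute) difference = 0.408 × √(2/π) = 0.33 week.
- 95% range = ±1.96 × 0.408 = ±0.80 week (±0.90 with 20 per arm, ±0.73 with 30).

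**Step 2: what that adds to the estimate**

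| Assumed slope (µV/week) | Typical (× 0.326) | 95% limit (× 0.80) | Chance that age alone adds ≥ 0.5 µV in favour of MBI |
|---|---|---|---|
| 0.25 | 0.08 µV | 0.20 µV | < 0.1% |
| 0.5 | 0.16 µV | 0.40 µV | 0.7% |
| 1.0 | 0.33 µV | 0.80 µV | 11% |

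For an imbalance at the 95% limit to supply the whole 1 µV, the slope would have to be 1/0.80 = 1.25 µV per week; for half of it, 0.62. In the extreme case of half the infants tested at each end of the window (SD 2.5 weeks), these become 0.72 and 0.36.

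**Step 3: what adjustment gains in precision**

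Residual SD after adjustment = √(SD² − (slope × 1.443)²), and the 95% half-width is 1.96 × SD × √(2/25), using normal quantiles.
- SD 3, slope 1: age explains 2.08/9 = 23% of the variance. The half-width falls from 1.96 × 3 × 0.283 = 1.66 to 1.96 × 2.63 × 0.283 = 1.46 µV. The variance ratio 9/6.92 = 1.30 equals about 30% more infants.
- SD 5, slope 0.5: age explains 0.52/25 = 2.1% of the variance, so the gain is negligible.

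**Step 4: chance of reaching 1 µV with no true effect**, 1 − Φ(1/(SD × √(2/25))), using the residual SD when adjusted

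| Assumed SD (µV) | Age ignored | Adjusted, slope 0.5 | Adjusted, slope 1 |
|---|---|---|---|
| 2 | 4% | 3% | 0.5% |
| 3 | 12% | 11% | 9% |
| 5 | 24% | 24% | 23% |
| 8 | 33% | 33% | 33% |
| 10 | 36% | 36% | 36% |

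Adjustment changes the answer materially only in the low-SD, steep-slope corner. Elsewhere ordinary sampling error dominates, and only an interval beside the estimate shows it.

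**The case against.** The strongest reply has five parts.

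1. **Random error, not bias.** Allocation is randomised, and those who collect or quantify outcomes are blinded. A chance age difference is ordinary sampling variation, like any other unadjusted prognostic factor. This stands.
2. **The endpoint is a contrast.** Each infant's value is mother's voice minus stranger's voice, so age effects common to both voices cancel. This stands in part: age-related change in telling the voices apart does not cancel, and that is what the measure is meant to capture.
3. **No slope is documented.** A reader might infer that age differences can supply much of the 1 µV. The documents do not support that. It needs an imbalance near the 95% limit together with a slope of roughly 0.6 to 1.25 µV per week under uniform ages, and no slope is given.
4. **The wording is consistent.** A reader might also see a conflict between one month and 43–48 weeks. Sections 1.2 and 3 equate the two, and the version 6.0 remark is a change-log note outside section 9. There is no contradiction. The remark nevertheless rests on no analysis in the documents.
5. **Age at ERP arises after randomisation.** Section 2.2 cites music listening as shortening hospital stays, so an effect on visit timing cannot be excluded outright. This is a small but fair caveat, and it is why an estimate without age should be shown as well.

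The R61 phase is also expressly exploratory, which limits the weight of the point but does not remove a cheap improvement.

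**Conclusion.** The point holds as a matter of precision. The test window is five weeks wide, the milestone rests on raw arm means, and neither age at test nor the stratification factor enters the analysis.

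With 25 per arm and uniform test ages, both assumed, the noise from age is typically 0.08 to 0.33 µV and reaches 0.2 to 0.8 µV at the 95% limit, over assumed slopes of 0.25 to 1.0 µV per week. The upper figures are tail values at a steep assumed slope and should not be read as the expected effect. The gain from adjustment ranges from negligible to about 30% in effective sample size (SD 3, slope 1), and more only if the SD is lower still or the slope steeper. The result of the milestone should not be called biased on this ground. The modest change is still worth making, because it is nearly free and settles the handling of age before the data are seen.

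**What to change.** In section 9.5, Measure 2, specify:

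- The arm difference is estimated from a linear model of each infant's mother-minus-stranger Late Slow Wave amplitude on arm, sex and corrected age at ERP (in days).
- The estimate is reported with its 95% CI beside the 1 µV threshold, which stays as it is.
- Age at ERP is summarised by arm, and the estimate without age is shown as a sensitivity analysis, because test age is fixed after randomisation.

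**Cost.** A few lines of text and two degrees of freedom. Sex is already needed for randomisation. The documents do not list age at test as a variable, but it follows from gestational age at birth (section 6.2.1) and the visit date, so no new assessment is required. The remaining drawback is the post-randomisation caveat, which the sensitivity analysis makes visible.

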6.2.5 Music Based Intervention or Control Sessions

Targeted averaged 4-5 sessions of MBI or Control will be played per week. With each session of intervention, evaluations of vital signs and MBI information will be obtained. Target 6 weeks of MBI or control (+/- 1 week).

- Vital Signs
- MBI Information

7. SAFETY ASSESSMENTS

7.1 Specification of Safety Parameters

Study coordinators will monitor for any distress from music: finger splay, grimace, vital sign disturbance, or persistent crying. If crying lasts longer than 5 minutes, the intervention will be stopped for that session.

7.2 Methods and Timing for Assessing, Recording, and Analyzing Safety Parameters

NA

7.3 Adverse Events and Serious Adverse Events

An **adverse event (AE)** is generally defined as any unfavorable and unintended diagnosis, symptom, sign (including an abnormal laboratory finding), syndrome or disease which either occurs during the study, having been absent at baseline, or if present at baseline, appears to worsen. Adverse events are to be recording regardless of their relationship to the study intervention.

A **serious adverse event (SAE)** is generally defined as any untoward medical occurrence that results in death, is life threatening, requires inpatient hospitalization or prolongation of existing hospitalization, results in persistent or significant disability/incapacity, or is a congenital anomaly.

The main adverse effects that may occur during the study are:

Distress resulting from music based intervention and mild skin irritation or discomfort from EEG/ERP electrodes. NICU and research staff will be instructed to observe for signs of distress lasting more than five minutes during music based intervention that do not appear to be associated with other co-occurring interventions or conditions. Signs of distress will include finger splay, grimace, vital sign disturbance, or persistent crying. If these signs of distress last longer than 5 minutes, music based intervention will be stopped for that session and this event will be reported to the PI. Routine skin monitoring and cares will be performed by NICU staff and research coordinators while EEG leads are in place. Care will be taken when placing the brain net for EEG or 128-channel Geodesic Sensor net for ERP to avoid discomfort.

7.4 Reporting Procedures

A core group from the research team consisting of the PI, co-investigators, and statisticians will be responsible for ongoing monitoring of the trial. They will also be responsible for reporting any issues regarding the safety of the study or threats to data integrity to the IRB.

All adverse events will be reported to the PI immediately or within 24 hours. The PI will report adverse events that meet University of Minnesota IRB reporting requirements to the IRB per IRB guidelines. We do not foresee any serious adverse events from participation in this minimal-risk music-based intervention study. For each adverse event (serious or non-serious), the investigator will provide the onset, duration, intensity, treatment, action taken, and outcome. The investigator will determine the relationship of the adverse event to the study-related procedures. Study coordinators will enter safety monitoring and adverse event data into the electronic database. Eligibility verification and data completion will be monitored by the research coordinator and PI.

7.5 Follow-up for Adverse Events

The PI will record all reportable events with start dates occurring any time after informed consent is obtained until 7 (for non-serious AEs) or 30 days (for SAEs) after the last day of study participation. At each EEG/ERP study visit, the investigator will inquire about the occurrence of AE/SAEs since the last visit. Events will be followed for outcome information until resolution or stabilization.

7.6 Safety Monitoring_

This research study involves no greater than minimal risk to participants. All participants will be monitored by the Principal Investigator (PI) and study coordinators.

A Data Safety Monitoring Board (DSMB) has been convened for this study. It is an independent group of experts charged with reviewing study data for subject safety, study conduct and progress, and providing formal recommendations regarding study continuation, modification, and termination.

The University of Minnesota CTSI Independent Monitor(s) will review study materials (documents, records, drug/device accountability, Case Report Forms, etc.) to assure that the study is conducted, recorded, and reported in compliance with FDA Good Clinical Practice.

